The objective of this phase IIb RCT is to determine the efficacy and safety of a compensatory intervention designed to improve daily activity performance and participation outcomes in preparation for a definitive trial. We will test the hypothesis that a manualized, theoretically grounded, and empirically supported transition intervention (COMPASS) is superior to an equivalent dose of attentional control (AC) for daily activity performance and participation outcomes with high adherence. The hypothesis is based on our previous work,^{35,36} the work of others,^{27,57,58} and our preliminary data. We will recruit 180 patients currently undergoing IR for IS or focal ICH and randomize them to receive five in-home sessions (one pre-discharge visit and four post-discharge visits) and two booster contacts of the enhanced rehabilitation transition program or AC. Our primary endpoint of participation and secondary outcome of ADL performance will be assessed by certified blinded raters at baseline, immediately after intervention, and at 6 and 12 months after stroke. Measures of mobility, cognition, and depression, will be used to characterize the clinical phenotype or body structure and function of the participants as important covariates. We will also examine important process outcomes such as cost, satisfaction, adherence, safety, and caregiver burden.

Study Participants

Stroke patient inclusion criteria: (1) aged ≥ 50 years, (2) acute IS or focal ICH diagnosis, (3) independent ADLs prior to stroke (premorbid Modified Rankin Scale Score ≤ 2), (4) plan to discharge to home.

Stroke patient exclusion criteria: (1) severe terminal systemic disease that limits life expectancy to < 6 months,

(2) previous disorder (e.g., dementia) that makes interpretation of the self-rated scales difficult or SBT score of 10 or less (indicating significant cognitive impairment), (3) moderate-to-severe aphasia as determined by the NIHSS Best Language rating of 2 or more, (4) reside in congregate living facility.

Caregiver inclusion criteria: (1) primary informal (family or friend) caregiver of a stroke patient enrolled in the COMPASS II study, (2) aged ≥ 18 years

Caregiver exclusion criteria: (1) non-English speaking

TRISL staff:

Inclusion criteria: (1) occupational therapist, physical therapist, or case manager at TRISL, (2) provided treatment to stroke patient enrolled in the COMPASS II study

Exclusion criteria: (1) Non-English speaking

Recruitment

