Timing: *Pre-discharge Environmental Modification Intervention.* Using standardized assessment and manualized procedures, environmental modifications will be installed before discharge. The intervention (not reimbursable) will be provided at no cost to the participant. *Post-discharge Activity and Participation Intervention.* On completion of T1b phone assessment, the participant will receive visits 2–5 over an 8-week period. Interventions will progress in complexity from daily activities to community participation based on the participant's goals. A booster session will be provided at 4 and 5 months after intervention over the phone; participants may request a home visit.

Attention Control Group

The control group will experience the same effects of time and attention in the home but no effect on the outcome of interest.⁷⁴ Because this study examines the efficacy of a new intervention, there is no opportunity for a usual care arm with dose equivalency. Because 75% of stroke survivors and 78% of caregivers report that their informational needs were not met in the hospital,⁷⁵ we developed and piloted a tailored stroke

education program for AC. An OT practitioner will deliver the program in accordance with “Evidence-Based Educational Guidelines for Stroke Survivors after Discharge Home.”⁷⁶ Topic order is determined by participants. Four 75-minute sessions will be provided. Topics include stroke symptoms, risk factors and preventing stroke recurrence, nutrition, managing emotions, sleep, fatigue, pain, social support, and sexuality. Written materials from the National Stroke Association and the American Stroke Association are provided. Environmental barriers will not be addressed in the educational sessions.

Follow-up Period for All Participants

Stroke and caregivers: Home visits T2 (immediately after intervention), T3 (6 months after stroke), and T4 (12 months after stroke). The follow-up activity, participation, and process assessments will be conducted in the home. All follow-up assessments will be completed by a blinded rater who did not conduct the T1 evaluation, as new home modifications could reveal group assignment. Distal time points will explore the permanency of any treatment effect on participation. If the participant is not available for in-home assessment, the primary endpoint will be collected by phone. Falls and healthcare utilization are collected **monthly** by phone (using an automated system).

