For participants who experience a delay in the study timeline (such as hospital admission, travel, short-term admission to a skilled nursing facility, etc.), the timeline will be adjusted accordingly. For example, if someone returns to the hospital during the intervention period and is in the hospital for 4 weeks, their T2 follow-up will be pushed back 4 weeks. If we can't schedule the T3 for three months past the normal time point for the T3, we will skip the T3 and schedule the T4.

Our primary outcome of the study is community participation. This has been severely limited by the current COVID-19 pandemic stay-at-home orders. We will adjust some of our follow up timepoints for data collection to reflect the SAH orders and allow people a chance to get back into the community before collecting community participation data. Our original timepoints are as follows: T2 (immediate post treatment), T3 (six months post stroke) and T4 (12 months post stroke). We will collect data at those timepoints but we are adding an additional collection time for each of those. Our T2COVID, T3COVID, T4COVID are all 60 days after the original T2/T3/T4 time point to allow for the SAH orders to lift and the participant to resume normal community participation. We will adjust these timepoints if the SAH orders continue longer than anticipated at this point.

Waiver of Consent: Retrospective Chart Review

At this time, we have consent to review medical charts during the enrollment and treatment process. However, we do not have permission to review the record after treatment was completed. Because we have ceased recruiting and all of our participants are finished with their participation in the study intervention and control groups, we no longer have contact with the majority of study participants. We would like to review medical charts (Wash U BJH medical records only) from participants who signed the Wash U COMPASS II consent form. We will collect limited data points, including date of death, hospitalizations, emergency room visits, and SNF/IPR admissions between their date of enrollment in this study and date of final study contact. For the waiver of consent, we will recruit participants already enrolled in this study.

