NIH Toolbox Instrumental Support Scale measures the availability of support for an individual to assist with completing daily tasks; 8-item scale, uses a 5-point likert scale response, scores are summed with higher score indicating more instrumental support.

10-Item Connor-Davidson Resilience Scale will measure resilience or ability to adjust to a stressful situation; consists of 10 items, all answered used a 5-point likert scale; total scores range from 0-40, with higher scores indicating greater resilience.

Healthcare Utilization and Mortality

Retrospective review of the medical records of all randomized participants to collect date of death, hospitalizations, emergency room visits, and skilled nursing facility (SNF)/Inpatient Rehabilitation (IPR) admissions between participants' date of enrollment until date of final study contact as a follow up metric to identify patient outcomes (see waiver of consent).

Statistical Analyses

Intention-to-Treat Analysis

We will perform our analyses using an intention-to-treat paradigm. We will perform exploratory data analysis looking for extreme or otherwise unusual values. Non-normal and heteroscedastic data will be transformed as necessary.

Baseline Analyses

We will use unpaired *t* tests and chi-square tests to compare T0 and baseline characteristics in the two groups for descriptive information (except when statistical assumptions are not met, in which case we may use Wilcoxon or Fisher exact tests).

Missing Data

We expect missing values in outcome measures because of dropout, death, missed assessment, or nonresponse. Our main analysis, a linear mixed-effects model, accommodates missingness due to treatment, prior outcome, or baseline covariates missing at random.⁸² Assuming that missing data occur at random, inferences will be valid even if we have differential dropout by intervention arm. If the missing data mechanism is not ignorable (ie, missing is not at random), then mixed-effects selection models or pattern-mixture models will be used.⁸³

Primary Analysis

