Our primary analysis (testing primary hypothesis) will be based on a linear mixed model using baseline and 12-month RNLI s, accounting for the correlation between a participant's repeated measurements over time. The fixed-effect portion of the model will have the form $Y_{it} = \beta_0 + \beta_1 \times 12\text{ months} + \beta_2\text{Group} + \beta_3\text{Group} \times 12\text{month}$, in which Y_{it} is the RNLI score for participant i at baseline (time 0) and 12 months (time 1), and *Group* indicates study arm. In this model, the baseline RNLI is modeled as a dependent variable.²⁷ For improved precision, the model will be adjusted for baseline covariates including race, sex, depression, and length of hospital stay if an imbalance in covariates between arms is observed in baseline analyses. In this model, β_0 is the mean RNLI score for the control arm at time 0, and β_1 is the change in the mean RNLI from baseline to time 1 for the control

arm; β_2 is the mean RNLI score for the treatment arm at time 0, and β_3 is the change in mean RNLI from time 0 to time 1 for the treatment arm. The primary hypothesis is that the difference in the change in RNLI scores from time 0 to time 1 between arms will be tested by examining β_3 , which estimates the difference.

Secondary Analyses

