For the secondary analyses of the change in SIS score at 1 year and the change in I-HOPE at 1 year, we will use the same approach as for the primary analysis because these two outcomes are also continuous. We have overall type I error control for testing the 1-year change in these three analyses at the design stage. The significance level for testing is 0.016. In addition to comparison of 1-year change, we will extend the model by including scores immediately after intervention and at 6 months to see whether the difference in outcomes is achieved at those time points. Depending on the form of time variable in the model, we will use appropriate regression coefficients or a linear combination of the regression coefficients to determine the difference in change of these scores between arms at certain time points. Interpretation of these results should be cautious because we do not have the type I error controlled for these analyses. Because it is possible that severity of functional impairment after stroke may impact response to treatment, we will analyze impact of functional impairment on response to treatment. We will examine functional impairment by group interaction to examine possible differential intervention effects of functional impairment on community participation and performance of daily activities.

Safety

To determine whether the intervention poses no greater risk than AC, we will examine the differences in numbers of falls and rehospitalizations between groups. The statistical models for count data will be used for analyses of these two outcomes. Using the number of falls as an example, we will fit a Poisson regression model (with overdispersion adjustment if necessary), in which a dummy variable for the intervention arm is used. The regression parameter estimate for this dummy variable is the log of rate ratio of falls for COMPASS versus control arm, and exponentiation of the regression parameter estimate is rate ratio. Using the parameter estimate and its standard error, we can construct a two-sided 95% CI for the rate ratio. We expect the confidence interval for rate ratio will include 1, indicating no significant difference in the fall rate between the two groups.

Process Outcomes

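### The primary model uses only baseline and 12-month RNLI, so dropout that follows the T2 or 6-month score is not covered, and the Missing Data section claims more than this model supports

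*Combined protocol and SAP*

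**What the plan says.** - **Primary Analysis:** the model is "a linear mixed model using baseline and 12-month RNLI". It has two times only, and "the baseline RNLI is modeled as a dependent variable". Baseline covariates enter only if the arms look imbalanced.
- **Missing Data:** the main model "accommodates missingness due to treatment, prior outcome, or baseline covariates missing at random". Assuming data are missing at random, "inferences will be valid even if we have differential dropout by intervention arm". Selection or pattern-mixture models are reserved for non-ignorable missingness, with no stated trigger.
- **Research Design Overview:** the primary endpoint is "assessed by certified blinded raters at baseline, immediately after intervention, and at 6 and 12 months after stroke", so two further RNLI scores are due before month 12.
- **Follow-up Period for All Participants:** "If the participant is not available for in-home assessment, the primary endpoint will be collected by phone". When T3 is long overdue, "we will skip the T3 and schedule the T4". COVID repeat visits are added 60 days after T2, T3 and T4.
- **Secondary Analyses:** "we will extend the model by including scores immediately after intervention and at 6 months". The purpose is to look at the earlier time points, and the section warns that type I error is not controlled there.

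**The concern.** Whether missingness can be ignored depends on what the likelihood contains. In the two-visit model the term prior outcome can mean only baseline RNLI. The scores closest in time to a missed 12-month visit, T2 and 6 months, are left out. A participant who leaves after a poor 6-month score is missing at random given everything collected, but not given what the primary model uses.

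Nothing else in the plan clearly closes the gap. The extended model is not the primary test. The selection and pattern-mixture fallback is worded for non-ignorable data, and dropout explained by recorded scores would not clearly trigger it. The covariates are baseline measures that enter only conditionally, so the claim about baseline covariates also holds only when the imbalance rule brings them in.

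At stake is the 12-month arm contrast. Participants know their group (World Health Organization Data Set, masking entry), so reasons for leaving could differ by arm. That is the situation in which the Missing Data section promises valid inference.

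**Working it through.** **Plan inputs** (Sample Size Calculations; Secondary Analyses). The plan states no bias figure to reproduce.

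- Effect: 15.3 − 1.3 = 14.0 points.
- Change SD: √[(22.6² + 23.4²)/2] = √529.2 = 23.0.
- Retained at 30% attrition: 180 × 0.70 = 126, or 63 per arm.
- Standard error of a completer change-score difference: 23 × √(2/63) = 4.1.
- Test level: 0.016, two-sided.
- The stated 130 for RNLI does not follow from 0.016 and 80% power, which give 118 by the Welch test. That is a separate matter and is not used below.

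**Why the two-visit model fails.** Its estimate of the 12-month mean in arm g is

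ȳ₁₂(observed) + b × [ȳ₀(all) − ȳ₀(observed)],

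where b is the pooled slope of 12-month on baseline RNLI. To first order, the bias in each arm is the mean, among those observed, of the 12-month residual after regression on baseline. It is zero if dropout depends on arm and baseline only. If dropout depends on the 6-month score, it is non-zero whenever the 6- and 12-month scores are correlated given baseline. The bias of the contrast is the difference between arms, so equal biases cancel.

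**Assumptions not in the documents.** Correlations at lags 1/2/3 between the four visits are 0.70/0.55/0.40, 0.50/0.50/0.50, 0.80/0.70/0.60 and 0.70/0.49/0.343. Per-visit SD is 23/√[2(1 − r)], with r the baseline-to-12-month correlation:

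- r = 0.343: 23/√1.314 = 20.1
- r = 0.60: 23/√0.80 = 25.7

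The 6- to 12-month correlation given baseline is then:

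- (0.70 − 0.55×0.40)/√(0.6975×0.84) = 0.63
- (0.50 − 0.25)/0.75 = 0.33
- (0.80 − 0.70×0.60)/√(0.51×0.64) = 0.67
- (0.70 − 0.49×0.343)/√(0.7599×0.8824) = 0.65

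So the omitted scores carry real information about the missing ones.

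**Simulation.** Normal data were generated at T1b, T2, 6 and 12 months. Logistic dropout depended on the latest RNLI, either before every visit or only after T2, with 30% missing at month 12 unless stated. There were at least 150,000 participants per arm. Both models were fitted by maximum likelihood with a common covariance.

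| Dropout pattern | Bias of two-visit contrast (points) |
|---|---|
| Depends on T1b only, opposite slopes by arm | about 0 |
| Same rule in both arms, log-odds 1 per SD, null true | 0 |
| Same rule in both arms, log-odds 1, effect 14 | about 0 to −1.0, depending on whether dropout rates also match |
| One arm only, log-odds 0.5 | 0.5 to 1.2 |
| One arm only, log-odds 1 | 0.8 to 2.4 |
| Same slope of 1, 40% v 20% missing | 0.7 to 1.7 |
| Opposite slopes of 1 | about 2.3 to 4.7 |

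If low scorers leave, the contrast moves down when control is affected and up when COMPASS is affected. If high scorers leave, the signs reverse. The four-visit model stayed within about 0.25 throughout, which is simulation error.

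Relative to the planned effect, log-odds 1 in one arm gives 0.8/14 = 6% to 2.4/14 = 17%, and log-odds 0.5 gives 0.5/14 = 4% to 1.2/14 = 9%.

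**At N = 180, level 0.016**, control-arm dependence at log-odds 1, first three structures, 1,500 replicates:

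- Two-visit type I error: 0.020 to 0.026.
- Power at 14 points: 0.76 to 0.79 for two visits, 0.86 to 0.91 for four.

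**Steeper dependence** (slope 1.5; baseline/follow-up and between-follow-up correlations of 0.3/0.5, 0.5/0.7 and 0.7/0.8): bias was 2.9 to 4.0 points with control only affected and 6.1 to 8.0 with opposite slopes. Four-visit bias was about 0.1 or less.

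**Non-informative dropout:** the four-visit model lowers the variance by only about 2 to 8%. The case for it rests on bias, not efficiency.

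**The case against.** - **The validity sentence is conditional on missing at random.** If dropout depends only on arm and baseline RNLI, it is correct for this model. That stands: the text overreaches by not naming the outcomes it conditions on, and is not false on every reading.
- **The fallback could apply.** Relative to the two-visit model, dropout following T2 or 6-month RNLI is non-ignorable, so selection or pattern-mixture models might be read as covering it. With no trigger stated, this cannot be relied on, and such models are a roundabout substitute for using the recorded scores.
- **The extended model is already planned.** It could yield a 12-month contrast, but the plan does not assign it that role.
- **The sizes depend on assumptions.** Process Outcomes targets 80% retention for COMPASS, and telephone collection should limit missing 12-month scores. At 20% missing, one-arm bias is about 0.8 to 1.6 points for log-odds 1 and 0.4 to 0.9 for 0.5, against a standard error near 4. The power loss shown is for control-arm dependence. With COMPASS-arm dependence and low scorers leaving, the error is an inflated estimate instead. This changes the size, not the conclusion.
- **Timing.** The waiver-of-consent section says recruitment has ceased and all participants have finished study treatment. A late change of primary model needs care, which the fix allows for.

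**Conclusion.** The concern holds. The primary model protects against dropout explained by arm, baseline RNLI and any covariates actually included. It does not protect against dropout that follows T2 or 6-month RNLI, so the Missing Data section claims more than this model supports. That conclusion comes from the text and does not depend on simulation.

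The size does depend on it: about 0.8 to 2.4 RNLI points at 30% missing with one arm affected at log-odds 1, less for weaker dependence or less missingness, and more if the arms differ in opposite directions. The bias can go either way. It is near zero when rule and rate match across arms, and the documents do not establish that dropout would differ. This is an inexpensive improvement that should be made, not a defect that invalidates the trial.

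**What to change.** **Before any unblinded analysis**, make the extended model primary: RNLI at T1b, T2, 6 and 12 months, categorical visit by arm, unstructured covariance and all available visits, including participants whose T3 was skipped. Test only the 12-month arm-by-time contrast, at the planned 0.016. Keep the T2 and 6-month contrasts descriptive. State whether the original or the COVID-repeat score enters at each visit, and how delayed visits are assigned. Use the same model for SIS, and for I-HOPE where its visits were collected.

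**If unblinded analysis has already taken place**, keep the two-visit model primary and report the four-visit 12-month contrast as a labelled sensitivity analysis.

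**In either case**, reword the Missing Data section to name the outcomes and covariates the model conditions on, keep the sensitivity analyses for missingness that depends on unobserved scores, and state how deaths are handled.

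**Cost:** SAP wording, a visit-mapping rule (which the planned extension needs anyway) and a few more covariance parameters. No new data or new type of model is needed. The change does not address death or dropout driven by unobserved scores.

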Prior to randomization, baseline activity assessment will be conducted in the home before discharge by an OT using methods established in our pilot study. The intervention is designed to augment rather than replace usual care, so both groups will receive the in-home assessment (considered best practice). Medically stable participants who are eligible for a therapeutic pass will participate in the home visit. The OT provider will meet the participant and their family at TRISL for car transfer training before departing for the participant's home. The visit will be scheduled to avoid disrupting ongoing inpatient therapy and to accommodate family schedules. Transportation will be provided via study staff vehicle, family vehicle or taxi cab. If the participant is *not* able to transfer safely into a family vehicle or if no family or vehicle is available, we will charter a wheelchair-accessible taxi. If the entrance to the home is not accessible, a temporary ramp will be installed. We were able to install ramps within 48 hours of request in our pilot trial. Onsite, we will use I-HOPE to identify environmental barriers in the home and to establish baseline activity levels. Results of the T1 home assessment (for participants in *each arm*) will be shared with the rehabilitation health care team, because home assessment is considered best practice for patients whose disposition is home.⁶⁰

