Participants will be allocated using a 1:1 ratio via adapted randomization sequences generated *a priori* by the study statistician, [name], using a computerized formal probability model. The allocation ratio will be maintained at periodic intervals. Randomization sequence concealment will be achieved by query of the REDCap (Research Electronic Data Capture) system.⁶³ After baseline assessment (T1) is securely uploaded and locked and stratification variables are entered, the interventionist will elicit the treatment assignment in the field in real time using a secure data connection to REDCap. This will permit prioritization of problems for participants assigned to the treatment group.

Upon randomization, participants will be assigned to an interventionist by the treatment coordinator. Although the results of the home assessments will be shared with the rehabilitation staff, IR staff will be blinded to the group placement so that they do not modify their inpatient or discharge treatment plan. All outcomes will be assessed by a blinded rater.

Phone Assessment T1b

To allow time for participants to adjust and personally assess their participation, T1 participation assessments will be conducted for both groups by telephone 2 days after discharge from IR. A rater who is blinded to allocation will conduct the baseline assessment for the primary, secondary, and exploratory endpoints.

Upon completion of T1b phone assessment, the participant will receive visits 2–6 over an 8-week period. The home modification group will progress from daily activity performance to community participation.

Primary Intervention

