Evaluate acceptability and feasibility to aid in the interpretability of the trial. COMPASS will have high acceptability (80% retention), high fidelity by therapists (95% of elements and 90% of dose delivered), low safety risk (no increased rate of falls or health care use compared with the AC group), and high adherence (80% of modifications in use) at 12 months. We will conduct between-group comparisons of process endpoints collected at each time point (time to first fall, number of injurious falls, health care utilization rate, dosage delivered, and adherence rate) using unpaired *t* tests or chi-square tests. We will compare the characteristics of patients who complete the assigned intervention with those who do not for differences in stroke severity and comorbidities. Descriptive statistics will be used for costs per participant and adherence.

Sample Size Calculations

The study is designed to have 80% of power to reject three null hypotheses of equal mean changes in the primary and secondary endpoints (RNLI, SIS, and I-HOPE) using a two-sided, two-sample, unequal-variance *t* test with overall type I error <0.05 . Three alternative mean changes (standard deviation [SD] of change) in intervention and control populations are 15.3 (SD 22.6) versus 1.3 (SD 23.4) for RNLI, 15.7 (SD 16.1) versus 5.6 (SD 9.1) for the SIS ADL domain, and 62.1 (SD 26.1) versus 46.2 (SD 18.8) for I-HOPE. With a 1:1 allocation ratio, 130 patients (65 in each group) are needed for the RNLI outcome, 84 are needed for the SIS outcome, and 100 are needed for the I-HOPE outcome. We will enroll 180 patients to account for a 30% attrition rate. This magnitude of between-group difference is considered clinically meaningful based on prior relevant literature and is achievable based on our pilot study. Sample size calculation includes correlation between baseline and follow-up measures and is based on analysis of change scores, which is equivalent in efficiency to the proposed analytic model. Based on the number of stroke patient participants, we will enroll an equivalent number of caregivers.

Strengths and Limitations

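### The primary model leaves the baseline means of the arms free and so tests a change score; baseline-adjusted estimation would be at least as precise, most cleanly for I-HOPE

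*Combined protocol and SAP*

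**What the plan says.** The Primary Analysis section specifies a linear mixed model for RNLI at two times, with an intercept, a 12-month term, a Group term and their product. The baseline score is an outcome: "In this model, the baseline RNLI is modeled as a dependent variable". Of the Group coefficient the text says that it "is the mean RNLI score for the treatment arm at time 0". As the model is written, that coefficient is the difference between arms at time 0. On either reading each arm has its own baseline mean, and no equality constraint is stated. The test is on the interaction: "the difference in the change in RNLI scores from time 0 to time 1 between arms will be tested by examining" that coefficient. Baseline RNLI is not a covariate. The listed covariates are conditional: "including race, sex, depression, and length of hospital stay if an imbalance in covariates between arms is observed in baseline analyses".

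For SIS and I-HOPE, Secondary Analyses says "we will use the same approach as for the primary analysis because these two outcomes are also continuous", at a significance level of 0.016. Sample Size Calculations bases the numbers on change scores, "which is equivalent in efficiency to the proposed analytic model".

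The baselines are taken at different times. At the home visit before randomisation (Baseline Home Visit), "Onsite, we will use I-HOPE to identify environmental barriers in the home and to establish baseline activity levels". For participation, under Phone Assessment T1b, "T1 participation assessments will be conducted for both groups by telephone 2 days after discharge from IR". By then assignment has been drawn (Randomization and Blinding), and modifications may already be in place (Primary Intervention).

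**The concern.** A model with baseline as an outcome is not a problem in itself; a constrained-baseline model does the same. The issue is the free Group term. With it, the two-time-point model gains nothing from the correlation between baseline and follow-up beyond what a change score gains. A change score subtracts the whole baseline value, noise included. An adjusted analysis subtracts only the part that predicts follow-up. The plan looks for extra precision from race, sex, depression and length of stay, yet does not adjust for the baseline outcome score, which is already collected.

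At stake is precision on the three endpoints tested at 0.016. For RNLI and SIS there is a second matter: the change score removes in full any arm difference already present at T1b.

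**Working it through.** **Inputs.** From Sample Size Calculations, the mean changes (SD of change) are: RNLI 15.3 (22.6) versus 1.3 (23.4), difference 14.0; I-HOPE 62.1 (26.1) versus 46.2 (18.8), difference 15.9. The test is a two-sided unequal-variance t test. Alpha is 0.016. With 180 enrolled and 30% attrition, 180 × 0.7 = 126, or 63 of 90 per arm. The correlation rho and the raw SDs are not given. I assume rho of 0.3, 0.5 and 0.7, and equal SDs at both times within each arm.

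**The plan's own figure.** At alpha 0.016 and 80% power, the RNLI inputs need 59 per arm, against the stated 65. With 65 per arm, change-score power is 84.6%. The stated number is therefore larger than its inputs require; why is a separate question.

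**Complete data.** Let s0 and s1 be the SDs at baseline and 12 months.
- Change score: variance s0² + s1² − 2·rho·s0·s1.
- Adjusted: variance s1²(1 − rho²).
- The gap is (s0 − rho·s1)², which is never negative. It is zero only when the within-arm slope b = rho·s1/s0 equals 1.
- With equal SDs the ratio is (1 + rho)/2 = 0.65, 0.75, 0.85.

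A simulation with 90 per arm at rho 0.5 agrees: SE 3.497 for both the change score and the planned model, and 3.009 for ANCOVA.

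**With dropout.** The planned mixed model also uses participants who have only a baseline. Relative to the completers' change score, its variance is [(1 + rho) + (1 − rho) × 63/90]/2:
- rho 0.3: (1.3 + 0.49)/2 = 0.895
- rho 0.5: (1.5 + 0.35)/2 = 0.925
- rho 0.7: (1.7 + 0.21)/2 = 0.955

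Adjusted relative to planned: 0.65/0.895 = 0.73; 0.75/0.925 = 0.81; 0.85/0.955 = 0.89. Simulation with 28% missing at rho 0.5 gave SEs of 3.98 (change score), 3.85 (planned) and 3.48 (adjusted).

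**Power, 63 completers per arm.** The SE of the completers' change contrast is √[(22.6² + 23.4²)/63] = 4.10 for RNLI and √[(26.1² + 18.8²)/63] = 4.05 for I-HOPE, with power of 83% and 93%. Multiplying by the square roots of the factors above gives:

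| Endpoint | rho | SE planned | SE adjusted | Power planned | Power adjusted |
|---|---|---|---|---|---|
| RNLI | 0.3 | 3.88 | 3.30 | 88% | 96% |
| RNLI | 0.5 | 3.94 | 3.55 | 86% | 93% |
| RNLI | 0.7 | 4.01 | 3.78 | 85% | 90% |
| I-HOPE | 0.3 | 3.83 | 3.27 | 95% | 99% |
| I-HOPE | 0.5 | 3.90 | 3.51 | 95% | 98% |
| I-HOPE | 0.7 | 3.96 | 3.74 | 94% | 96% |

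The RNLI rows assume no arm difference at T1b, so that both analyses estimate the same 14 points. SIS has little to gain: its change-score power is already 97%.

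**Unequal SDs.** If the 12-month SD is 1.25 times the baseline SD, the complete-data ratios are 0.78, 0.89 and 0.98. At 1.5 times with rho 0.7 the ratio is 0.998 and the slope is 1.05.

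**Late baseline.** If treatment has shifted T1b by e, the change score loses e and ANCOVA on T1b loses b × e. That is less for b between 0 and 1, and more for b above 1.

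**The case against.** The strongest reply is that the plan is adequate as it stands. Endpoint by endpoint, power exceeds the 80% target even on completers' change scores, and type I error is not affected. That stands, and it limits the point to efficiency.

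A second reply is that the gain is easily overstated. Setting the adjusted analysis against completers' change scores (83% for RNLI, 93% for I-HOPE) ignores that the planned mixed model also uses participants with only a baseline. This is right, and the comparison above is with the planned model. The size also rests on a correlation and an SD ratio that the documents do not give.

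Third, T1b follows randomisation, so adjusting for it conditions on a value that treatment may have affected. This is a good reason not to impose equal baseline means on RNLI or SIS. It does not favour the planned model, which uses T1b at full weight. It does not apply to I-HOPE at T1.

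A reader might go further and infer that the late baseline will cost the trial a definite part of its 14-point RNLI effect. The documents do not support that. They give no early shift, and the 14 points are a difference in change, not a 12-month difference from which a shift could be subtracted. Nor can one infer that adjustment is always less biased: that requires a slope between 0 and 1.

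**Conclusion.** The point holds as a precision recommendation. With complete data the planned model is a change-score analysis, and baseline adjustment is at least as precise in large samples. Under equal SDs, 63 of 90 completers per arm and rho from 0.3 to 0.7, the variance falls by about 27% to 11%. The gain shrinks as the 12-month SD rises above the baseline SD, and vanishes at a slope of 1. The case is cleanest for I-HOPE, where a baseline before randomisation justifies equal means by design. For RNLI and SIS, adjustment for T1b may lessen the removal of an early effect but does not eliminate it. None of this makes the design a failure.

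**What to change.** **I-HOPE.** Drop the Group main effect, so that baseline means are equal, or use ANCOVA on the T1 score. State that T1 is the I-HOPE baseline. Where the COVID procedure moved the first I-HOPE to a visit after discharge, by which time modifications may be in place, treat that baseline as missing.

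**RNLI and SIS.** Replace the change contrast with the 12-month difference between arms. Report it twice: with T1b as a covariate, and without T1b but adjusted for the age and FIM score used in randomisation. Name which version is primary before unblinding.

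**Cost.** No new data are needed. Enrolment is closed, so the change needs an SAP amendment that is dated, and shown to be dated, before unblinding. The T1b-adjusted version still conditions on a value taken after randomisation, which is why the version without T1b should stand beside it.
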